#### 5.1.2.2 Oxaliplatin

Patients will receive FOLFOX chemotherapy before and after radiation and after surgery per treating physician's discretion

Oxaliplatin is commercially available as an aqueous solution in vials containing 50 mg and 100 mg at a concentration of 5 mg/mL. The vials do not contain any preservative and they are intended for single use.

Intact vials should be stored at room temperature. Solutions diluted in D5W are stable for 6 hours at room temperature or 24 hours under refrigeration.

The calculated dose of oxaliplatin (85 mg/m^2 in this protocol) should be diluted for infusion with 250 mL to 500 mL D5W. Oxaliplatin should not be diluted with a sodium chloride solution. Needles, syringes, catheters or IV administration sets containing aluminum should not be used with oxaliplatin. As with other platinum compounds, contact with aluminum may result in a black precipitate.

Oxaliplatin will be administered by intravenous infusion over 2 hours. Infusion time may be prolonged (up to 6 hours) in patients experiencing pharyngolaryngeal dysesthesia or mild grade 1 delayed hypersensitivity reactions. Oxaliplatin is unstable in the presence of chloride or alkaline solutions. Do NOT mix or administer oxaliplatin with saline or other chloride-containing solutions. Do NOT administer other drugs or solutions in the same infusion line. Flush IV lines/catheters with Dextrose 5% in Water both before and after oxaliplatin administration.

### **5.1.3 Other Modality(ies) or Procedures**

#### **5.1.3.1 Radiation Therapy**

##### **Radiation Therapy Schema:**

The target dose to the pelvic PTV is 25 Gy with 5 Gy in 5 fractions during one week. The boost volume is included. An extra boost of 2 Gy x 2 – 3 is also possible to deliver in certain circumstances.

##### **Target volumes**

###### **Boost GTV**

Gross tumor volume (GTV) is the visible primary tumor and visible pathological lymph nodes.

###### **CTV boost**

GTV boost plus a margin of 2 cm within the same anatomical compartment as the tumor is in, for the dose from 45 to 50.4 Gy, also around radiologically engaged lymph nodes! If the tumor is entirely within mesorectum with no threatened MRF, the 2 cm extension for uncertainties in tumor spread does not need to go outside the fascia. The margin of 2 cm will thus chiefly be

added cranially and caudally. If the tumor e.g. grows into the sacral bone or the urinary bladder, the 2 cm margin does apply within those organs.

GTV boost plus a margin of 1 cm within the same anatomical compartment if an additional boost is given above 50.4 ( or 50.0) or 25 Gy.

### **Pelvic CTV**

1. The primary tumor
2. Primary lymph nodes in the bowel wall and within mesorectum. Mesorectum is composed of the surrounding fat around the bowel and extends dorsally towards sacrum. Distally, only lymph nodes or tumor deposits up to 4 cm are included. For tumors in lower rectum this means that the entire mesorectum down to the pelvic floor is included whereas in tumors high up in rectum, the most distal part of mesorectum is not included. The reason for this is to diminish radiation towards the sphincters.
3. The closest secondary lymph node stations consisting of presacral nodes and nodes along the rectal superior artery. These lymph nodes are partly overlapping with the primary mesorectal lymph nodes and they are important for all tumors within the rectum. Since local recurrences are very unusual above S1 – S2, lymph nodes above this level should not be included unless there are signs of pathological lymph nodes presacrally. If this is the case, the cranial limit of CTV should be at least 1 cm above the most cranial pathological lymph node.
4. The lateral lymph node stations along the medial rectal and obturator arteries until they reach the level of the obturator canal should be included if the primary tumor is below the peritoneal reflection or up to about 8 to 10 cm from the anal verge. In higher tumors, these nodes are rarely involved.
5. The lateral lymph node stations also include lymph nodes along the internal iliac artery up to the bifurcation from the external iliac artery. The cranial border for the CTV is in most cases just below the bifurcation of the internal and external iliac arteries. In most patients this is at the level of S1 – S2. In certain individuals, the bifurcation can be above L5 – S1. In these instances the cranial CTV border is at the level of S1-S2, unless lymph nodes along the internal iliac artery is seen. Then a margin of at least 1 cm above the most cranial lymph nodes must be drawn.
6. Inguinal lymph nodes are included in CTV only if the tumor grows into the anal canal and distal to the dentate line or if it grows into the distal part of vagina.
7. The entire ischio-rectal fossa, the anal canal and peritoneum is included in pelvic CTV only if the tumor grows into the levators or down into the anal canal. In these instances, rectal excision is always required.

8. Lymph nodes along the external iliac artery are included if the tumor grows into anterior organs like the prostate, urinary bladder, cervix, vagina or uterus to such an extent that the external nodes are at risk for metastases. Therefore, napping or minimal overgrowth dorsally is not sufficient.

## PTV

The above description relates to the CTV. A PTV should normally be defined and includes CTV and internal target volume (ITV) and a margin necessary for the setup. These margins are depending upon several factors that are related to the equipment at the radiotherapy center.

## Treatment verification

Treatment verification should be performed according to institutional guidelines. Acceptable deviations should be in line with the chosen CTV-PTV margin.

### 5.1.4 Investigational Imaging Agent Administration

N/A

## 5.2 **Definition of Dose-Limiting Toxicity**

Dose limiting toxicities (DLTs) will be captured until completion of FOLFOX chemotherapy (weeks 18/19) and will be graded according to the CTCAE ver 5. DLTs will be defined as clinically significant grade 3 or 4 toxicities possibly or probably related to study treatment. The following AEs will not be considered DLTs:

- any grade of alopecia,
- grade 3 arthralgia or myalgia,
- brief (< 1 week) grade 3 fatigue,
- grade 3 fever
- grade 3 diarrhea or vomiting responding to supportive care.
- grade 3 radiation dermatitis

All patients who have received at least one dose of the study regimen are evaluable for toxicities; for dose escalation decisions, patients should have completed  $\geq 80\%$  of the planned chemotherapy and radiation doses unless the reason for discontinuation is an AE that qualifies for DLT.

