## SCHEMA

- Patients with rectal adenocarcinoma either locally advanced or metastatic rectal adenocarcinoma requiring chemoradiation to the primary lesion are eligible.
- Patients with locally advanced rectal adenocarcinoma (T3 or T4, at risk of having a positive surgical radial margin and/or N+), or patients with metastatic disease requiring chemoradiation.
- Patients will be treated with FOLFOX chemotherapy x 4 doses over 8 weeks (weeks 1-8) followed by short course radiation over 5 days (weeks 9 or 10).
- Subsequently, starting approximately 2 weeks after finishing short course RT, patients will receive FOLFOX chemotherapy x 4 doses (weeks 12 / 13 – 19 / 20). While surgical resection of the primary is not mandatory, those requiring surgery will undergo resection 8-16 weeks later (weeks 27 - 36) and / or further systemic therapy per treating physician's discretion.
- Talimogene laherparepvec will be administered via endoscopy by a qualified physician for a total of 4 doses at the following time points: a) week prior to c1 FOLFOX b) weeks 3, 5 and 7 during FOLFOX
- Dose escalation will be done using a 3 + 3 design over 2 cohorts and a total of 15 patients

Dose level+	TALIMOGENE LAHERPAREPVEC Dose (PFU/ml)	Capecitabine (mg/m  po bid on days of radiation)	Radiation	Comments
1	1x 10  , 1x 10  , 1x 10  , 1x 10 	825	50.4 Gray in 28 fractions	Completed prior to protocol amendment 1/23/21
1 (amended)	1x 10  , 1x 10  , 1x 10  , 1x 10 	N/A	25 Gray in 5 fractions	To be implemented if DLTs noted with DL 2
2	1x 10  , 1x 10  , 1x 10  , 1x 10 	N/A	25 Gray in 5 fractions	

will be treated at MTD.

Dose limiting toxicities (DLTs) will be captured until completion of FOLFOX chemotherapy (weeks 18/9) and will be graded according to the CTCAE ver 5.0.

#Patients with inadequate archival tissue for integrated biomarker analysis

^As part of pre-surgical evaluation or at a corresponding time point in patients not undergoing surgery

+Dose escalation will be done using a 3+3 design for a total of 15 patients that will be treated at MTD

TVEC = talimogene laherparepvec

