#### Toxicity

Nausea, diarrhea, vomiting (mild); stomatitis: 5-8 days after treatment initiation; myelosuppression: granulocytopenia (9-14 days); thrombocytopenia (7-14 days); alopecia; loss of nails; hyperpigmentation; photosensitivity; maculopapular rash; palmar-plantar erythrodysesthesias: (42-82% receiving continuous infusion); CNS effects: cerebral ataxia (rare); cardiotoxicity: infarction, angina; asymptomatic S-T changes 68%; ocular effects: excessive lacrimation and less commonly, tear duct stenosis.

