## Toxicity

The most commonly observed oxaliplatin toxicities include neurotoxicity, GI toxicity, and myelosuppression. Three neurotoxicity syndromes have been seen: acute sensory neuropathy develops within hours to 2 days after oxaliplatin administration. Symptoms include paresthesias, dysesthesias, and hypoesthesia of the hands, feet and perioral region. Jaw spasm, abnormal tongue sensation, dysarthria, eye pain and a sensation of chest pressure have also been noted. Acute sensory neuropathy symptoms may be exacerbated by exposure to cold temperature or cold

objects. Symptoms are reversible, usually resolving within 14 days and commonly recurring with further dosing. This syndrome has been observed in about 56% of patients receiving oxaliplatin with 5-FU and leucovorin.

Acute pharyngolaryngeal dysesthesia is reported to occur in 1-2% of patients. This syndrome is characterized by a subjective sensation of difficulty breathing or swallowing without laryngospasm or bronchospasm or objective evidence of hypoxia. Avoidance of cold drinks, food and air is suggested in order to minimize pharyngolaryngeal dysesthesia. Antianxiety agents (e.g., lorazepam) may be used to treat pharyngolaryngeal dysesthesias once oxygen saturation has been documented to be normal.

Peripheral neuropathy persisting > 14 days is characterized by paresthesias, dysesthesias, and hypoesthesia. Abnormalities in proprioception may also be seen. Symptoms of persistent neuropathy may improve upon discontinuation of oxaliplatin.

Gastrointestinal toxicities include nausea, vomiting (oxaliplatin is considered to be moderately emetogenic) and diarrhea.

Neutropenia is reported in 73% of patients receiving oxaliplatin with 5-FU and leucovorin (44% grade 3 or 4). Grade 3 or 4 thrombocytopenia is reported to occur in 4% of patients receiving the combination.

Allergic reactions, similar to those seen with other platinum compounds, have also been observed in patients treated with oxaliplatin. Reactions range from rash to anaphylaxis.

Rarely, oxaliplatin has been associated with pulmonary fibrosis, which may be fatal. Oxaliplatin should be discontinued in the presence of unexplained pulmonary symptoms (e.g. nonproductive cough, dysphagia) or pulmonary infiltrates until interstitial lung disease or pulmonary fibrosis have been ruled out.

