Dose level	Talimogene laherparepvec Dose (PFU/ml)	Capecitabine (mg/m  po bid on days of radiation)	Radiation
1	10  , 10  , 10  , 10 	825	50.4 gray in 28 fractions
1 (amended)	1x 10  , 1x 10  , 1x 10  , 1x 10 	N/A	25 Gray in 5 fractions (To be implemented if DLTs noted with DL2)
2 (amended)	10  , 10  , 10  , 10 	N/A	25 Gy in 5 fractions

Talimogene laherparepvec will be administered via endoscopy by a qualified physician for a total of 4 doses as before but at the following amended time points: a) week 1 prior to initiation of FOLFOX chemotherapy b) weeks 3, 5 and 7 during FOLFOX chemotherapy.

In addition to monitoring patients for AEs related to talimogene laherparepvec, injection site will be evaluated directly during endoscopy at subsequent time points such as during pre-surgical evaluation and in those forgoing surgery needing endoscopic surveillance.

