### 5.1.2 Other Agent(s)

#### 5.1.2.1 5-Fluorouracil

Patients will receive FOLFOX chemotherapy before and after radiation and after surgery per treating physician's discretion

5-FU is commercially available as a 50 mg/mL solution for injection in 10 mL, 20 mL, 50 mL and 100 mL vials. Inspect for precipitate; if found, agitate or gently heat in water bath. Bolus injections are prepared using undiluted drug. 46 hour infusion of 5-FU should be prepared for administration via ambulatory infusion pump according to the institution's standards. These solutions may be prepared in D5W or 0.9% NaCl. 5-FU should not be mixed in the same solution with most parenteral antiemetics.

Intact vials should be stored at room temperature and protected from light. Slight yellow discolor does not usually indicate decomposition. Stability in ambulatory pumps varies according to the pump, manufacturer of drug, concentration and diluent. Please refer to appropriate reference sources for additional information.

In this study, 5-FU is administered as a 400 mg/m^2 IV bolus followed by 2400 mg/m^2 by IV infusion over 46 hours starting immediately after the bolus.

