	a:	Albumin, alkaline phosphatase, total bilirubin, bicarbonate, BUN, calcium, chloride, creatinine, glucose, LDH, phosphorus, potassium, total protein, SGOT [AST], SGPT [ALT], sodium.										
	b:	Serum pregnancy test (women of childbearing potential).										
	c:	Off-study evaluation.										
	d:	At baseline and subsequently as required per treating physician's discretion										
	e:	Tumor markers include CEA and CA 19-9 at baseline, if above normal, repeat within 1 week of day 1 of radiation and with presurgical evaluation										
	f:	Chemotherapy regimen / dosing / schedule, imaging and follow up post-surgery per treating physician's discretion										
	g:	Evaluation by any involved provider (medical oncology / surgical oncology and / or radiation oncology)										
	h:	Adverse event evaluation until 4 weeks out of surgery										
	i:	Optional										
	j:	In patients without adequate archival tissue										
	k:	Radiation will be 25 Gy over 5 fractions.										
	l:	Refer to Section 9 for tube types and volumes.										
	m:	On day 1 of each cycle of FOLFOX										
	n:	In those deemed needing surgical resection per clinical evaluation; not mandatory per protocol										

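### On the weeks 18/19 wording, DLT capture ends in the week of the eighth FOLFOX dose, so delayed toxicity of that cycle largely falls outside it; the schema and calendar run the block to weeks 19/20, which would cover it

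*Combined protocol and SAP*

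**What the plan says.** Section 5.2 sets the window: "Dose limiting toxicities (DLTs) will be captured until completion of FOLFOX chemotherapy (weeks 18/19"). The schema has the same rule with what looks like a misprint: "will be captured until completion of FOLFOX chemotherapy (weeks 18/9"). Section 5.1 lists the eighth FOLFOX dose under weeks 18/19.

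The schema describes the post-radiation block differently: "patients will receive FOLFOX chemotherapy x 4 doses (weeks 12 / 13 – 19 / 20"). The column in the Section 10 calendar also runs to weeks 19/20. Footnote m to that column places the assessments "On day 1 of each cycle of FOLFOX".

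For timing of toxicity, the 5-FU part of Section 2.3 gives "stomatitis: 5-8 days after treatment initiation; myelosuppression: granulocytopenia (9-14 days); thrombocytopenia (7-14 days"). For oxaliplatin, Section 2.3.1 says that "acute sensory neuropathy develops within hours to 2 days after oxaliplatin administration".

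Adverse events in general are collected until 4 weeks after surgery (Section 10, footnote h), but nothing ties that collection to DLT status. DLT counts drive the MTD rule (at most 1 DLT in 6 patients, Sections 5.2 and 13.1) and the rule that halts enrollment when one third or more of patients at the dose have a DLT (Sections 5.3 and 13.1).

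**The concern.** The window is tied to the end of dosing, not to a number of days after the last dose. If completion of FOLFOX means the week in which dose 8 is given, cycle 8 is the only cycle not followed through the protocol's own onset times for myelosuppression. Grade 3-4 toxicity of the backbone treatment is in scope: Section 5.2 counts clinically significant events related to study treatment, and neutropenia and thrombocytopenia are not on its list of exclusions.

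A febrile neutropenia 10 days after dose 8 would then be reported as an adverse event but left out of the count behind the primary endpoint. Missed events can only lower that count. Because the documents give two end weeks for the same block, two sites could also classify the same event differently.

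**Working it through.** **1. The stated week.** Dose 5 is in weeks 12/13 (Section 5.1). Three further doses at 2-week intervals: 12 + 6 = 18 and 13 + 6 = 19. This reproduces weeks 18/19 for dose 8, so the stated end of the window is the dosing week itself. Dose 7 is in weeks 16/17, so cycles 1-7 are each followed for at least 14 days.

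**2. Onset times laid on cycle 8.** Assumptions: dose 8 falls on the first day of its week and counts as day 1, and the 5-FU onset times apply to each cycle. The 5-FU is given "by IV infusion over 46 hours starting immediately after the bolus", so it ends on day 3.

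| Window closes at | Acute neuropathy (hours to 2 days) | Stomatitis (5-8) | Thrombocytopenia (7-14) | Granulocytopenia (9-14) |
|---|---|---|---|---|
| End of infusion, day 3 | inside | outside | outside | outside |
| End of dosing week, day 7 | inside | inside except day 8 | outside except day 7 | outside |
| End of weeks 19/20, day 14 | inside | inside | inside | inside |

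If the ranges count days elapsed after the dose, each delayed event moves one day later. Thrombocytopenia is then wholly outside the dosing week, and the last day of the two 14-day ranges falls one day past the end of weeks 19/20. A limit written in days avoids this ambiguity.

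**3. Illustrative size for neutropenia.** Section 2.3.1 cites 44% grade 3-4 neutropenia with oxaliplatin, 5-FU and leucovorin, without a number of cycles. Assume that total accrues over eight cycles at a constant per-cycle hazard. The share of all patients whose first event is in cycle 8 is (1 - T)^(7/8) - (1 - T), where T is the eight-cycle total:
- T = 0.44: 0.56^(7/8) - 0.56 = 0.602 - 0.560 = 0.042.
- T = 0.20 (assumed lower case): 0.80^(7/8) - 0.80 = 0.823 - 0.800 = 0.023.

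**4. Effect on the decision rules.** The documents do not give the share f of all DLTs that arises late in cycle 8, so a range is assumed. The captured rate is q = p(1 - f), where p is the true DLT rate. A dose level passes the 3+3 rule with probability (1-q)^3 + 3q(1-q)^2 × (1-q)^3. The one-third rule needs at least 5 DLTs in 15 patients (binomial). At p = 0.30:

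| f | q | P(level passes 3+3) | P(at least 5 of 15) |
|---|---|---|---|
| 0 | 0.300 | 0.494 | 0.485 |
| 5% | 0.285 | 0.525 | 0.433 |
| 12.5% | 0.2625 | 0.573 | 0.355 |
| 25% | 0.225 | 0.654 | 0.234 |

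For scale, step 3 gives 0.042/0.44 = 9.6% and 0.023/0.20 = 11.5% of neutropenia events. The share across all DLTs would be smaller to the extent that other DLTs arise earlier.

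**5. Check on Section 13.1.** The chance of at least one DLT in 15 patients at a rate of 0.167 is 1 - 0.833^15 = 0.935, which matches the stated 93.5%. With f = 12.5%, q = 0.146 and the chance is 0.907.

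**The case against.** The best defence is that the operative words are completion of FOLFOX, with the weeks only in parentheses. The schema counts a block through the second week of its last cycle: doses in weeks 1, 3, 5 and 7 are described as weeks 1-8. By the same convention the second block ends in weeks 19/20, and completion would cover days 8-14. This reading is plausible, and on it the fault is a mismatched label. It cannot be settled from the text, because Section 5.2 attaches weeks 18/19 to completion and the schema's own DLT sentence follows it.

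Several stronger readings are tempting, and the documents do not support them:
- **No toxicity of the last cycle can count.** Acute neuropathy is inside the window on every reading, and events on days 5-7 are inside if the dosing week is covered. It is also wrong to say that one cycle in eight goes unobserved.
- **The protocol gives a 5-14 day onset range for FOLFOX.** It gives three separate ranges, for 5-FU only.
- **About 7% of patients would have a missed first event.** That is the hazard among patients still event-free, 1 - 0.56^(1/8) = 0.070, not the share of all patients.
- **The escalated agent is under-observed.** Talimogene laherparepvec is last given in week 7 ("weeks 3, 5 and 7 during FOLFOX chemotherapy"), 11-12 weeks before the cut-off.
- **Toxicity peaks after the last cycle.** No section says so.

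Continued adverse event collection and the sponsor's data review before new dose levels would make a late event visible. Neither makes it a DLT.

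**Conclusion.** The point holds in limited form. On the 18/19 wording, delayed toxicity of cycle 8, chiefly myelosuppression, largely escapes the DLT definition. On the 19/20 wording it is covered. The plan supports both, so a day-10 event has no determined status in the count behind the primary endpoint.

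The illustrative size is about 4% of patients with a first grade 3-4 neutropenia in cycle 8, or about 2% if the eight-cycle total is 20%. This rests on a constant per-cycle hazard and on spreading the cited 44% over eight cycles. It ignores the dose holds, reductions, growth factor and withdrawals in Section 6.2, and fewer events would be DLTs because only clinically significant ones count.

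The effect is confined to the tail of one of eight backbone cycles. In cohorts of 3 and 6, however, a single uncounted event can turn 2/6 into 1/6 and so change the MTD, and the error runs towards accepting a dose level. The correction should be made, and it needs only a change of wording.

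**What to change.** - In Section 5.2 and the schema, state the end of DLT capture once, as a number of days after the last FOLFOX dose that covers the protocol's own onset times: 14 days, that is, the end of cycle 8, or earlier removal from therapy.
- Reconcile the week numbers for the post-radiation block and for the DLT cut-off across the schema, Sections 5.1 and 5.2 and the calendar, including the misprint in the schema.
- State that MTD, de-escalation, expansion and one-third-rule decisions are made only after each patient concerned has reached that point, using the adverse event collection already planned.

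**Cost:** wording in four places. Each remaining decision waits about 1-2 weeks longer, and slightly more events may count as DLTs. Level 1 is complete and level 2 is the top level, so no upward escalation step is delayed.

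The definition can change without a new visit. The calendar has no end-of-therapy visit tied to dose 8: the off-study evaluation includes a blood count but has no fixed timing. If the sponsor also wants a scheduled count in the 14 days after dose 8, that would be an added assessment and a separate choice.

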### **AEs that are considered “Dose Limiting” for talimogene laherparepvec**

- 1) Herpetic events that should be considered DLTs:
  - Serious herpetic events such as herpetic encephalitis, encephalomyelitis or disseminated herpetic infection

- Any herpetic events confirmed due to talimogene laherparepvec that require treatment with acyclovir or similar anti-viral agent. Talimogene laherparepvec treatment should be held if systemic acyclovir or other anti-viral is indicated. If ongoing anti-viral treatment is required, talimogene laherparepvec treatment should be permanently discontinued
  - \* Herpetic events due to wild-type HSV-1 or wild-type HSV-2 which require acyclovir and are not due to talimogene laherparepvec (as confirmed by PCR testing) should not be considered as DLTs caused by talimogene laherparepvec.

2) DLT will also be defined as any of the following talimogene laherparepvec-related toxicity:

- Grade 2 or greater immune-mediated AEs.
- Grade 2 or greater allergic reactions.
- Any grade plasmacytoma
- Any other grade 3 or greater hematologic or non-hematologic toxicity, with the exceptions of:
  - any grade of alopecia,
  - grade 3 arthralgia or myalgia,
  - brief (< 1 week) grade 3 fatigue,
  - grade 3 fever,
  - grade 3 diarrhea or vomiting responding to supportive care.

For other study treatments, DLT will be defined as clinically significant (ie excluding any grade alopecia, grade 3 arthralgia or myalgia, < 1 week grade 3 fatigue, grade 3 diarrhea, nausea, vomiting responding to supportive care), grade 3 or 4 toxicities possibly or probably related to study treatment or AEs.

Management and dose modifications associated with the above adverse events are outlined in Section 6.

Dose escalation will proceed within each cohort according to the following scheme. Dose-limiting toxicity (DLT) is defined above.

Number of Patients with DLT at a Given Dose Level	Escalation Decision Rule
0 out of 3	Enter 3 patients at the next dose level.
≥2	Dose escalation will be stopped. This dose level will be declared the maximally administered dose (highest dose administered). Three (3) additional patients will be entered at the next lowest dose level if only 3 patients were treated previously at that dose.

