1 out of 3	Enter at least 3 more patients at this dose level. 

• If 0 of these 3 patients experience DLT, proceed to the next dose level.

• If 1 or more of this group suffer DLT, then dose escalation is stopped, and this dose is declared the maximally administered dose. Three (3) additional patients will be entered at the next lowest dose level if only 3 patients were treated previously at that dose.

≤1 out of 6 at highest dose level	This is generally the maximum tolerated dose, MTD. At least 6 patients must be entered at the MTD.

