## 7.2 Adverse Event Characteristics

- **CTCAE term (AE description) and grade:** The descriptions and grading scales found in the revised NCI Common Terminology Criteria for Adverse Events (CTCAE) version 5.0 will be utilized for AE reporting. All appropriate treatment areas should have access to a copy of the CTCAE version 5.0. A copy of the CTCAE version 5.0 can be downloaded from the CTEP web site  
[http://ctep.cancer.gov/protocolDevelopment/electronic\\_applications/ctc.htm](http://ctep.cancer.gov/protocolDevelopment/electronic_applications/ctc.htm)
- **For expedited reporting purposes only:**
  - AEs for the agent that are ***bold and italicized*** in the CAEPR (*i.e.*, those listed in the SPEER column, Section 7.1.1) should be reported through CTEP-AERS only if the grade is above the grade provided in the SPEER.

- Other AEs for the protocol that do not require expedited reporting are outlined in section 7.3.5.
- **Attribution** of the AE:
  - Definite – The AE is *clearly related* to the study treatment.
  - Probable – The AE is *likely related* to the study treatment.
  - Possible – The AE *may be related* to the study treatment.
  - Unlikely – The AE is *doubtfully related* to the study treatment.
  - Unrelated – The AE is *clearly NOT related* to the study treatment.

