**Expedited AE reporting timelines are defined as:**

- o "24-Hour; 5 Calendar Days" - The AE must initially be submitted electronically within 24 hours of learning of the AE, followed by a complete expedited report within 5 calendar days of the initial 24-hour report.
- o "10 Calendar Days" - A complete expedited report on the AE must be submitted electronically within 10 calendar days of learning of the AE.

Serious adverse events that occur more than 30 days after the last administration of investigational agent/intervention and have an attribution of possible, probable, or definite require reporting as follows:  

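### For FOLFOX and radiation toxicity, the DLT definition as written leaves out deaths and events attributed as Definite

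*Combined protocol and SAP*

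**What the plan says.** Section 5.2 gives the general rule: "DLTs will be defined as clinically significant grade 3 or 4 toxicities possibly or probably related to study treatment". Later in the section, the sentence covering the other study treatments (FOLFOX and radiation) ends with the same limits: "grade 3 or 4 toxicities possibly or probably related to study treatment or AEs". The clause for talimogene-related toxicity is worded differently: "Any other grade 3 or greater hematologic or non-hematologic toxicity, with the exceptions of" a short list. It has no upper grade and no restriction on attribution level, and Section 6.1 repeats it.

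Section 7.2 uses a five-level attribution scale whose top level stands apart from Probable and Possible: "Definite – The AE is *clearly related* to the study treatment". Where the protocol means all three related levels, it says so. The footnote to the expedited reporting table in Section 7.3.3 covers late serious events that "have an attribution of possible, probable, or definite require reporting as follows", and names grades 3, 4 and 5.

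Section 5.2 also sets evaluability for escalation. Patients should have completed at least 80% of planned chemotherapy and radiation "unless the reason for discontinuation is an AE that qualifies for DLT". The escalation table adds "At least 6 patients must be entered at the MTD", and Section 13.1 defines the MTD as the highest dose with at most one DLT in six patients.

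**The concern.** For toxicity attributed to FOLFOX or radiation and not to talimogene, the rule leaves out the worst grade and the surest attribution. A grade 4 event judged probably related is a DLT. A fatal one, or a grade 4 event judged definitely related, is not.

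Such events are foreseeable. The oxaliplatin toxicity text in Section 2.3.1 says "Rarely, oxaliplatin has been associated with pulmonary fibrosis, which may be fatal" and describes allergic reactions up to anaphylaxis, and Section 6.2 stops oxaliplatin for grade 3 or 4 hypersensitivity. An infusion reaction of that kind could reasonably be coded Definite. Much of the DLT window is also backbone treatment alone. Under Section 5.1 the last talimogene dose is in week 7, radiation follows in weeks 9/10, and four more FOLFOX doses run to weeks 18/19, when the window closes.

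The DLT count is the primary endpoint. It drives every 3+3 decision and the one-third stopping rule in the expansion, and the objective is the MTD of the combination, so backbone toxicity belongs in it.

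**Working it through.** **The plan's own figures.** Section 13.1 gives the chance of at least one DLT in 15 patients. 1 − (1 − 0.167)^15 = 0.935 and 1 − 0.70^15 = 0.995, matching the stated 93.5% and 99.5%. These take the DLT rate as given, so they do not depend on how a DLT is defined.

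**Is the gap closed elsewhere?** Sections 5.3, 6.1 and 13.1 add neither grade 5 nor Definite for backbone toxicity. Section 7.3.3 requires deaths to be reported but does not make them DLTs.

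**Effect on one cohort of six, with one other DLT.**

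- The omitted event comes after 80% of planned treatment: the patient stays as a non-DLT and the record reads 1/6 (accepted) instead of 2/6 (rejected).
- It comes before 80%: the patient is not evaluable, leaving 1 of 5. Six are required, so if a further patient is entered (an assumption; no replacement rule was found) and has no DLT, the record is again 1/6.

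**Probabilities.** A dose is acceptable as MTD with probability P(0/3)·P(≤1/3) + P(1/3)·P(0/3) = P(X ≤ 1), X ~ Bin(6, p).

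- p = 0.30 (used in Section 13.1): 0.70^6 + 6(0.30)(0.70^5) = 0.118 + 0.303 = 0.420
- p = 0.25 (dose 2 of scenario 2 in Section 13.1): 0.534

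Let u be the per-patient rate of omitted events. The documents give none, so u is assumed. The counted rate becomes p − u if the patient stays as a non-DLT, or (p − u)/(1 − u) if replaced. The chance that at least one of six patients has such an event is 1 − (1 − u)^6.

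| u | At least one in six | p = 0.30: stays / replaced | p = 0.25: stays / replaced |
|---|---|---|---|
| 0 (all counted) | – | 0.420 | 0.534 |
| 2% | 0.114 | 0.464 / 0.452 | 0.582 / 0.571 |
| 5% | 0.265 | 0.534 / 0.503 | 0.655 / 0.630 |
| 10% | 0.469 | 0.655 / 0.601 | 0.776 / 0.737 |

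These figures use the at-most-one-in-six rule for declaring the MTD. They are not comparable with the Section 13.1 table, which is approximately reproduced by letting a dose pass on 0/3 alone: (1 − p)^3 + 3p(1 − p)^5 = 0.494 at 0.30 and 0.600 at 0.25.

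**Secondary: exemption lists.** The general list in Section 5.2 is unconditional, so it already exempts fever and radiation dermatitis for every treatment. The one real mismatch is nausea responding to supportive care, which only the sentence on other treatments exempts.

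**Secondary: neutropenia.** This works in the opposite direction. No haematologic item is exempted, so grade 3 or 4 FOLFOX neutropenia literally counts, subject to the discretion in the clinical-significance qualifier. Section 2.3.1 gives a general rate of 44%, taken here as an upper bound because the holds, dose reductions and growth factor in Section 6.2 may lower it. The counted background rate is assumed, with no talimogene toxicity:

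| Background rate | Dose rejected, 1 − P(X ≤ 1) | At least 5 of 15 DLTs, given at most 1 in the first 6 | 0/3 observed |
|---|---|---|---|
| 20% | 0.345 | 0.0388/0.6554 = 0.059 | 0.512 |
| 30% | 0.580 | 0.0934/0.4202 = 0.222 | 0.343 |
| 44% | 0.824 | 0.1004/0.1762 = 0.570 | 0.176 |

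Section 2.4 reports no DLTs in the first cohort. For the three patients planned in Section 13.1, the last column shows that this does not settle the rate.

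**The case against.** The wording is probably a drafting slip, and investigators would likely count a treatment-related death whatever the text says. Expedited death reporting (Section 7.3.3), at least monthly calls (Section 12.1) and sponsor review before a new dose level (Section 13.1) make an unnoticed death unlikely. The gap also opens only when talimogene attribution is excluded, and a note in Section 7.1.1.1 warns that talimogene may worsen the known toxicities of its partner agents, so many severe events could fall under the talimogene clause. The RP2D condition, that at least 80% of patients receive at least 80% of planned doses, is a further partial check. Finally, u is unsupported at its upper end: 10% means that a third of all DLTs at p = 0.30 (0.10/0.30), or 40% at p = 0.25 (0.10/0.25), are backbone-only and either fatal or Definite. At 2% the shift at p = 0.30 is only from 42% to 45–46%.

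The points on frequency and size stand. They do not alter the rule, because reporting and review steps do not redefine a DLT. A Definite grade 3 or 4 event is less conspicuous than a death, and overriding the text case by case would rest the primary endpoint on unwritten judgement. One patient short of planned dosing would not fail the RP2D condition (14/15 = 93%). The neutropenia question is separate and belongs to the clinical team.

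**Conclusion.** The concern holds and should be corrected. For toxicity attributed only to FOLFOX or radiation, the definition omits grade 5 and Definite events in two places, and the 80% evaluability rule can also take an early backbone death out of the escalation count. This conclusion rests on the text and does not depend on u. A single omitted event can reverse a dose decision. The average effect depends on an assumed rate: at a true DLT rate of 30%, acceptance rises from 42% by about 3 to 4 percentage points at u = 2% and by 18 to 24 points at u = 10%, with the lower figure in each pair also assuming replacement. Talimogene-related toxicity is not affected.

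**What to change.** In the general definition and in the sentence on other study treatments, both in Section 5.2, write: grade 3 or higher (including grade 5), possibly, probably or definitely related. Leave the talimogene-specific DLTs unchanged. An early backbone death then qualifies as a DLT, so the patient also stays evaluable for escalation.

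In the same edit, state that the general exemption list applies to all study treatments other than the talimogene-specific DLTs, and add nausea responding to supportive care. Ask the clinical team to state which haematologic events count, and have the statistician confirm that the implied background rate is consistent with the 16.7% target in Section 13.1.

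The cost is protocol wording, plus a recheck of DLT status and evaluability for patients already treated. Section 2.4 reports no DLTs and no treatment-related SAEs in the first cohort, so a change there is unlikely.
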